## **PROCEDURES.**

**Screening.** Individuals interested in participating in this study will either contact the study team independently or will complete a contact form permitting University of Michigan to contact them. Research Associates will communicate with interested participants via phone and will privately explain the purpose of the study. If potential participants are still interested in the study, Research Associates will invite them to complete an initial phone screening. Research Associates will obtain oral consent from potential participants before beginning the initial phone screening.

Potential participants who provide oral consent will complete an initial screening over the phone with a trained Research Associate. The phone screening will take about 8-10 minutes and will assess the initial inclusion criteria. The phone screen will include a depression screen (PHQ-2) administered by a trained Research Associate. Potential participants will also be asked screening questions regarding age, how long they have resided in Hillsdale, Lenawee, Jackson, Calhoun or Branch County, MI and their psychosocial treatment history. All persons who meet initial eligibility criteria, including scoring  $\geq$ 2 on the PHQ-2, will be invited to participate in a baseline interview to determine further eligibility. If potential participants are interested in moving forward with study participation, the RA will work with the potential participant to schedule a baseline interview at their convenience. Potential participants will not be remunerated for the screening phase of the study. Reasons for screening and baseline refusal will be collected and coded for use in data analysis.

**Consent.** Before completing the baseline interview, Research Associates (RAs) will obtain informed consent from all participants. The Research Associate will schedule a meeting with potential participants, either in

person or virtually, via secure, web-based videoconferencing software available through the University of Michigan (i.e., Zoom) to review the informed consent document and answer any questions potential participants have about the study. If potential participants would like to participate, they will provide informed consent. If RAs and potential participants meet in person, written, informed consent will be obtained. The participant and the RA will each keep a copy of the document for their records. If RAs and potential participants meet virtually, RAs will send the potential participant a REDCap survey link that includes the informed consent document. After reviewing the consent document, potential participants who would like to participate will electronically sign the document in REDCap. The RA will send also participants a copy of the consent document via email.

**Assessment Interviews.** All RCT participants (ROST and ECC) are to complete baseline, post-treatment (PT) and 3-month follow-up (FU) interviews (see Table 4., below). At FU, participants randomized to ROST also complete a qualitative interview focused on their perceptions of treatment. Supplemental questions will be included for participants who did not respond to ROST and those who dropped out of treatment to gather information on intervention acceptability, feasibility, and choice points. RCT participants will receive \$25 for each assessment interview completed. Each assessment interview will take approximately 2 hours. Participants randomized to ROST will also receive \$20 for completing the qualitative interview at the FU time point.

**Baseline Interview.** All participants who meet screening eligibility criteria and consent to participate in the research study, will complete a baseline interview to diagnose depression and comorbid psychiatric conditions and assess other psychometric and demographic variables (see Table 4). This interview will take approximately 2 hours to complete. The interview will be completed in person or over the phone or secure, web-based videoconferencing software available through the University of Michigan (i.e., Zoom). Participants will receive \$25 for completing the baseline interview. All baseline interviews will be completed by clinical interviewers that have clinical mental health experience and education and have received extensive training in interview-based measures.

**In-Session Measures.** Participants randomized to ROST will complete a series of measures after each ROST sessions. The measures will be completed via REDCap online survey software. If ROST is held in person, participants will complete the online measures on site via a tablet. If ROST is held virtually, RAs will administer the online measures using REDCap online survey software distributed via email for the participants to complete after the group, while still in the Zoom room with RAs. Participants will complete weekly depression ratings (PHQ-9) to track symptoms during ROST. If participants endorse suicidal ideation on the PHQ-9 (score >0 on Question 9), they will complete the Columbia-Suicide Severity Rating Scale (C-SSRS). C-SSRS scores will be calculated via the REDCap survey software and connected to the corresponding suicide risk level (established via C-SSRS). If measures are completed onsite via table, all participants who complete the C-SSRS will be prompted by the online survey software to check in with their group leader and a Research Associate who will review their scores and risk level. If measures are completed by phone with an RA, the RAs will receive the participant's C-SSRS score and the risk level in real time. If a participant is at low risk, the Research Associate will encourage them to call the local Psychiatric Emergency Service and to discuss feelings with family members. Participants who are at low risk for suicidal ideation will continue participating in ROST sessions and their suicidal ideation will be monitored weekly until it is minimal. If a participant is at moderate or high risk for suicidal ideation, the Research Associate will immediately connect them to clinical back up – either [name] or [name] – both of whom are licensed clinical social workers. The clinical back up will assess risk and develop a safety plan with the participant and the Research Associate. After the plan is developed, it will be documented by the Research Associate who will complete a text-entry action plan via the REDCap survey. Please see the Human Subjects Protection section for a detailed description of risk levels and associated action/safety plans. Participants randomized to ROST who experience clinical deterioration over time in treatment (as indicated by an increase of 5 points or more on the PHQ-9 for participants with scores of 10 or above) will be contacted by a study team member and referred to local resources that can provide an increased level of care. Participants will also complete the Automatic Thoughts Questionnaire and the Behavioral Activation for Depression Scale at each weekly ROST session. The Group Cohesion Scale will be completed during Sessions 1, 4, and 8 and the Expectancy Rating scale will be completed during Session 3.

**Follow-up interviews.** All participants who completed the baseline mental health assessment interview will complete interviews at post-treatment (PT) and at 3-month follow-up (FU) timepoints. These interviews will be completed in person, over the phone, or via secure, web-based videoconferencing software available via the University of Michigan (i.e., Zoom). Research Associates will administer the same measures at post-treatment and 3 month follow-up that were assessed during the baseline interview (see Table 4). Supplemental questions will be asked to participants randomized to ROST who did not respond to the treatment or dropped out of treatment. This will allow us to gather information on intervention acceptability, feasibility, and choice points. Participants will receive \$25 for completing follow up interviews. These interviews will take about 1.5 hours to 2 hours.

**Treatment Fidelity and Group Leader Competence.** To ensure fidelity, an independent assessor (IA: Masters-level clinician with CBT experience and study-specific training) will rate leader adherence and competence using a version of the Collaborative Study Psychotherapy Rating Scale-Cognitive Therapy and the Cognitive Therapy Scale adapted for this study. All RCT sessions will be audio-recorded with participant consent and rated by the IA for treatment adherence and leader competence. [name] and [name] will review audio-recordings and competency ratings. The IA will regularly attend research meetings to discuss findings. [name] and [name] will provide weekly supervision to group leaders. [name] and [name] will review recordings for coverage of content and group leader competence, addressing any issues during weekly supervision with group leaders. We will develop a plan to incorporate missing content into the next session.

**Maintenance of samples.** Strategies will be used to encourage attendance of group sessions and to complete follow up interviews. Reminder emails, calls and/or text messages, based on participant preference, will be sent the day before each group session to remind participants of the group meeting times or interview times. If a participant misses a session, they will be contacted by the group leader and/or the research associate. The study team will stress the importance of attendance for the group sessions. The study team will collect participant addresses, phone numbers and email addresses as part of the baseline assessment. This contact information will be updated regularly by the study team throughout the study period. Participants will also be asked to identify contact persons that do not live with the participant and will know the participants whereabouts, if the study team cannot reach the participant. Participants will also receive compensation for completing interviews and group sessions.

**ROST retention.** All participants randomized to ROST will receive a schedule of the dates and times for all 8 ROST sessions prior to (if group is virtual) or at Session 1 (if group is in-person). During session one, group leaders will emphasize the importance of attendance. If a participant misses a session, the group leader or a research associate will call the participant to discuss the reason for missing the session and to discuss potential barriers to attending future sessions. Additional contact information, described in Maintenance of Samples, above) will be collected at baseline and used to reach participants if group leaders cannot contact a participant using primary contact information.

**Assessment retention.** Participants will be assessed at post treatment and 3-month follow up time points. Participants will be asked to schedule their 3-month follow up interview at their post treatment interview. If the PT interview is in-person, the Research Associate will give participants a business card that includes their FU interview date and time, along with the location of the interview, and payment information. If the PT interview is virtual, the Research Associate will email the participant their FU interview date and time, along with the location/zoom link for the interview, and payment information. An online calendar invite will be sent to participants as well. *To retain participants during the follow up period, participants will be sent bi-weekly check-ins via mail, email, phone, or text (based on participant preference) to ensure that their contact information is up to date, and to remind them of their next interview.* Participants will be given the option to complete an interview at their home or virtually, if there are travel barriers.

**Group leaders and training.** The group leaders will complete training program developed by the study team. First, group leaders will complete a web-based training on CBT for Depression created by [name].

Next, the trainees will complete one full day of in-person training with [name] and [name]. This in-person training will include didactic modules on depression, cognitive behavioral therapy for depression, group facilitation skills and safety planning. After completing the didactic modules, the group leaders will complete a second day of in-person training focused on the ROST intervention. The training will include a review of the computer-assisted program, the group leader manual, and fidelity ratings. The group leaders will be asked to role play the core components of the intervention (cognitive restructuring, behavioral activation, relapse prevention) as well as key group leader roles/responsibilities, including introducing workbook exercises, leading weekly check-ins, and reviewing homework. At the end of the second day of in-person training, the group leader will complete the Cognitive Behavioral Therapy Knowledge Questionnaire. Gaps in knowledge will be addressed as needed by the study team. Throughout the RCT, the group leaders will receive ongoing supervision and training. All ROST sessions will be audio recorded. The audio recordings will be reviewed by both [name] and [name]. Weekly supervision will be held with [name], [name], and the group leader to review session audio tapes and address additional training needs.

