In addition, at first contact, participants will be provided with an information sheet detailing procedures for contacting investigators should their depressive symptoms, comorbid symptoms, or risk for harm to self or others become a source of concern. If any of the scheduled reassessments reveal worsening depressive symptoms, comorbid symptoms, or risk for harm to self or others, a repeat face-to-face assessment will be completed, including the PHQ-9, CSRSS, BDI, and MINI. If there is a clinically significant worsening on the PHQ-9 or CSRSS relative to the prior assessment, significant effort will be made to expedite entry into the best available treatment outside the research protocol.

*Treatment Non-Participation.* If a participant does not participate in a session they will be counseled by one of the group leaders and a plan will be put in place to encourage participation. If a participant misses three consecutive sessions and the group leader cannot reach them, the group leader will stop reaching out. Study team members will still reach out to invite the participant to complete follow up assessments and document their reasons for discontinuing treatment.

*Interference with group process.* If a participant interferes with the group process due to extremely disruptive behavior, the participant will be counseled to minimize interference. If the disruptive behavior persists, they will be removed from ROST treatment.

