#### *Protections for Participants with Suicide Risk*

The primary risk with the proposed study is suicide risk. This research will follow a comprehensive protocol for responding to suicide risk based on the University of Michigan Health System (UMHS) suicide risk assessment standards. In every case, if a participant is determined to be at risk for suicide, several steps will be followed: (1) ongoing contact with the participant will occur until risk is determined to be minimal; (2) the investigators will be informed immediately and continuously apprised of any changes/developments in the participant's risk for suicide; (3) all assessments, conversations, and steps taken with the participant to ensure safety will be thoroughly documented; (4) we will communicate with our IRB to determine the need for adverse event reporting, and any actions taken or outcomes will be reported to the IRB and NIH. All participants will be initially interviewed in-person by trained research associates who have clinical experience and graduate level mental health training. This methodology allows for intervention should suicide be a risk. Interviewing clinicians will be trained in risk assessment and will receive ongoing training throughout the course of the study. All participants will be assessed for suicide risk using the UMHS suicide risk assessment protocol. If a participant is determined to be at risk based on clinical assessment, the research associate will contact [name] or [name] by phone or text. If risk is determined during the intervention based upon results of measures completed electronically during sessions or via participant disclosure of suicidal ideation, group leaders will contact [name] or [name] by phone or text. In both cases, [name] or [name] will then contact the

participant immediately and further assess suicide risk. If risk is determined to be present, the standard clinical protocol for responding to suicide risk will be implemented.

The protocol is as follows:

(1) Mild Risk (e.g., suicidal ideation present without presence of current plan, low intent, presence of hope, no current means)

- a. The individual will be encouraged to call the local Psychiatric Emergency Service.
- b. The individual will be encouraged to discuss feelings with family members. Should family members be present at the time of the interview, their immediate involvement will be enlisted.

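### The weekly PHQ-9 and ideation screen are scheduled only at ROST sessions with no make-up when one is missed, and the rules for already-flagged participants who stop attending do not agree

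*Combined protocol and SAP*

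**What the plan says.** PROCEDURES, In-Session Measures, ties the weekly ratings to the session: "Participants randomized to ROST will complete a series of measures after each ROST sessions", and "Participants will complete weekly depression ratings (PHQ-9) to track symptoms during ROST". In person, "participants will complete the online measures on site via a tablet". For virtual groups the survey is emailed "for the participants to complete after the group, while still in the Zoom room with RAs". The same paragraph refers in passing to measures done by phone with a research associate, but no section says when that route is used. Table 4 lists the PHQ-9 at baseline, post-treatment, follow-up and the sessions, and nowhere else.

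Two safety rules depend on this rating. A score above 0 on item 9 leads to the C-SSRS. A rise of 5 points or more, for scores of 10 or above, is clinical deterioration.

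For absence, ROST retention gives the task to either a research associate or the group leader, who "will call the participant to discuss the reason for missing the session and to discuss potential barriers to attending future sessions". Treatment Non-Participation adds counselling and a plan to encourage participation, then: "If a participant misses three consecutive sessions and the group leader cannot reach them, the group leader will stop reaching out". After that, study team members still invite the person to follow-up assessments and record why they stopped.

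For participants with identified ideation, In-Session Measures says of those at low risk that "their suicidal ideation will be monitored weekly until it is minimal". Protections for Participants with Suicide Risk requires, whenever a participant is found to be at risk, that "ongoing contact with the participant will occur until risk is determined to be minimal".

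**The concern.** The protocol names suicide risk as the study's primary risk, and weekly monitoring is its main scheduled safeguard in the ROST arm during treatment. A participant who is absent has no PHQ-9, no item 9 and no C-SSRS that week. If absence sometimes accompanies worsening, which is plausible but not something the documents establish, the safeguard is missing where it may be needed most.

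There is also an operational problem. Staff dealing with someone rated low risk at Session 3 who then stops attending would find several sections that apply and no single course to follow.

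**Working it through.** The plan states no sample size, power or event count on this point. The check is mainly a cross-reading, with simple arithmetic for scale.

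**Step 1. A participant not yet flagged who misses sessions.** Each channel by which the protocol could detect new ideation or deterioration during treatment:

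| Channel | Section | Reaches a non-attender on a schedule? |
|---|---|---|
| Weekly PHQ-9, item 9, C-SSRS | In-Session Measures; Table 4 | No, taken at the session |
| Phone administration by a research associate | In-Session Measures | Mentioned, but not tied to missed sessions |
| Missed-session call | ROST retention | Call required; no symptom or risk measure stated |
| Counselling after non-participation | Treatment Non-Participation | No symptom or risk measure stated |
| Reports from leaders, participants or family | Clinical Deterioration | No, passive |
| Information sheet on contacting the investigators | Clinical Deterioration | No, participant must initiate |
| Separate safety-monitoring plan | Clinical Deterioration | Names the waiting and follow-up periods, not the treatment period |

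The suicide-risk section describes identification during the intervention through electronic in-session measures or the participant's own disclosure. A non-attender has only the second. The next scheduled PHQ-9 is at post-treatment.

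**Step 2. Size of the gap.** The intervention description gives 8 weekly sessions. Table 4 numbers them to 10; I use 8.

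- If the last session attended is *k*, scheduled ratings with no stated means of collection = 8 − *k*. Stopping after Session 3: 8 − 3 = 5. Never attending: 8 − 0 = 8.
- Average ratings lost at attendance *a* = 8 × (1 − *a*). The documents give no attendance rate, so these values of *a* are assumptions: 0.80 gives 1.6, 0.70 gives 2.4, 0.60 gives 3.2.
- Enrollment and Participants expects 82% of 103 people attending randomization to take part in their condition: 103 × 0.82 = 84.46, which agrees with the stated 84 (42 per arm). The remainder is 103 − 84 = 19, or 19/103 = 18%. With an equal split (assumed), that is 19/2 = 9.5, so 9 or 10 in ROST. If they attend nothing, they have no PHQ-9 between baseline and post-treatment. Partial attenders would add to this.

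**Step 3. A participant already flagged who stops attending.** The relevant provisions:

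| Section | What it requires |
|---|---|
| In-Session Measures | Low risk: weekly monitoring until minimal |
| Clinical Deterioration | Low risk: weekly monitoring while continuing in the intervention |
| Suicide-risk section, general steps | Contact until risk is minimal, in all at-risk cases |
| Suicide-risk section, mild risk | Research-team contact until minimal; no interval or instrument |
| Suicide-risk section, moderate risk | Daily phone contact until mild, then less often until minimal |
| Treatment Non-Participation | Group leader stops outreach after three consecutive misses without contact; open ideation not mentioned |

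The duty of contact continues. For low or mild risk, the sections do not agree on whether monitoring stays weekly once attendance stops. They do not say what instrument is used, or how the outreach rule applies to someone with open ideation.

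**The case against.** The strongest reply is that the suicide-risk section already governs flagged participants. It applies in all at-risk cases, assigns follow-up to the research team at each risk level until risk is minimal, and does not depend on attendance. At moderate risk it adds daily calls, and participants are told in advance that the authorities will be called if someone at risk cannot be reached. The stop-outreach rule binds only the group leader, and only after three consecutive misses without contact. It can coexist with research-team follow-up.

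This stands. A reader might infer that flagged participants fall out of monitoring when they stop attending, or that the outreach rule flatly contradicts the suicide-risk section. The documents support neither. What they show is differing wording on frequency and method, and a missing cross-reference.

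The reply does not cover participants not yet flagged, because those duties begin only once risk has been identified.

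It is also fair to say that group leaders are trained in safety planning and have clinical backup, that nothing forbids asking about symptoms on the missed-session call, and that control participants are risk-assessed only at post-treatment and follow-up. An unflagged ROST non-attender is thus no worse placed than the control arm. That limits the severity, but the protocol sets a weekly standard for ROST and does not say how to meet it in absence.

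A reader might further infer that symptom trajectories within ROST are biased towards improvement. The ratings will come from attenders, but the direction depends on why people are absent, which the documents do not show. Data Analyses plans no analysis of the weekly PHQ-9 series. The PHQ-9 and BDI are taken in both arms at baseline, post-treatment and follow-up, and that comparison does not rest on session attendance.

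**Conclusion.** The point holds in two parts. First, a ROST participant who misses sessions and has not been flagged has no scheduled PHQ-9 or ideation screen until post-treatment. This follows from the text and needs no assumption about attendance. Its size does: five ratings for someone stopping after Session 3, an average of 1.6 to 3.2 of eight at attendance of 80% to 60%, and possibly 9 or 10 ROST participants with none if the protocol's expected non-participants split equally and attend nothing. The documents do not allow an estimate of how many would be both absent and newly at risk.

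Second, for flagged participants who stop attending, contact is still required but the sections are inconsistent on how it is done. This is a safety-procedure gap that should be closed. It is not a threat to the primary comparison.

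**What to change.** 1. In In-Session Measures and ROST retention, state that when a session is missed the existing weekly PHQ-9, with the protocol's existing item 9 and C-SSRS step, is collected during the missed-session call, using the phone route with a research associate that In-Session Measures already mentions. Add this to Table 4.
2. Reconcile In-Session Measures, Clinical Deterioration, Treatment Non-Participation and Protections for Participants with Suicide Risk for flagged participants who stop attending: the monitoring interval, the instrument, who is responsible, and how the outreach rule applies when ideation is open. Which clinical rule applies is for the investigators to decide.

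The cost is a few minutes on a call already planned, plus cross-references. A research associate must make or join calls that a group leader might otherwise make alone, and clinical backup must be reachable outside session times. The call does not help with people who cannot be contacted; for those already flagged, that case has to be settled under item 2.

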targeting churches with sizable Hispanic and African American congregations. Therefore, we expect to recruit approximately 90% White participants; 5% Hispanic participants; and 5% African American participants.

**Removing Participants from the Protocol.** Based on our experience, removal of participants from the protocol for clinical reasons is expected to be very rare, and established procedures are available to appropriately respond to various forms of clinical deterioration. Participants may be removed from the trial for the reasons listed below. In each case, participants will be consulted regarding potential removal. Final judgment for participant withdrawal will be made via consensus of group leaders, PI: [name], and Co-I: [name]. Effort will be made to continue assessment of any participants removed from the trial. Withdrawn participants will be referred for the best available treatment outside the research protocol.

*Clinical Deterioration.* During the active intervention phase, participants who experience clinical deterioration over time in treatment will be evaluated and removed from the trial. Clinical deterioration is defined as significant worsening of depressive symptoms, based on a 5 point increase on the PHQ-9 for those with scores of 10 and above. These participants will be contacted by a study team member and referred to local resources that can provide an increased level of care. Worsening suicidality or comorbid conditions that are determined to compromise participant safety will also be grounds for participant removal. These concerns may come to our attention directly via the group leaders, participants, or family members. Additionally, participants who endorse any level of suicidal ideation on the PHQ-9 ( $>0$  on question 9) will complete the Columbia Suicide Severity Rating Scale (C-SSRS). Participants whose scores indicate low risk for suicidal ideation on the C-SSRS will continue participating in the intervention and their suicidal ideation will be monitored weekly during that time. Participants whose scores indicate moderate or high risk for suicidal ideation on the C-SSRS will be connected to clinical back-up, connected to appropriate resources, and monitored. A safety-monitoring plan will be in place for participants experiencing worsening severity during the waiting period prior to treatment assignment or during the follow-up period.

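### For suicide risk found in a ROST session, the protocol states two escalation rules that differ on whether a clinician reassesses a low-risk participant at once and on which role starts the contact

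*Combined protocol and SAP*

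**What the plan says.** **In-Session Measures (under Procedures).** A ROST participant who scores above 0 on PHQ-9 item 9 after a session completes the C-SSRS. On site, the participant is prompted to "check in with their group leader and a Research Associate who will review their scores and risk level". The low-risk action follows: "If a participant is at low risk, the Research Associate will encourage them to call the local Psychiatric Emergency Service". Talking with family is also encouraged, the participant stays in ROST, and ideation is checked weekly until minimal. For the higher levels: "If a participant is at moderate or high risk for suicidal ideation, the Research Associate will immediately connect them to clinical back up". The text then points elsewhere: "Please see the Human Subjects Protection section for a detailed description of risk levels and associated action/safety plans".

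**Clinical Deterioration (under Removing Participants from the Protocol).** The threshold is the same. "Participants whose scores indicate low risk for suicidal ideation on the C-SSRS will continue participating in the intervention", with weekly monitoring, whereas "Participants whose scores indicate moderate or high risk for suicidal ideation on the C-SSRS will be connected to clinical back-up". The role that makes the connection is not named.

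**Protections for Participants with Suicide Risk.** The trigger reads: "If risk is determined during the intervention based upon results of measures completed electronically during sessions or via participant disclosure of suicidal ideation". Group leaders then phone or text one of two named persons. That person reaches the participant straight away and assesses risk further. If risk is confirmed, a protocol with Mild, Moderate and High tiers applies. Whatever the level, the investigators are to be told at once, steps documented, and contact kept up until risk is minimal.

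**Clinical Backup (under the intervention arm).** Two licensed clinical social workers are available to group leaders if a participant worsens or suicidality is present. No risk level is named.

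**The concern.** The protocol calls suicide the main risk of the study. For one event, low C-SSRS risk found after a session, two parts of the document lead staff to different actions. A Research Associate working from In-Session Measures would give the encouragement, arrange weekly monitoring and regard the matter as handled. A group leader working from the suicide-risk section would call clinical backup, and a clinician would reassess the participant that day. At moderate or high risk both texts bring in a clinician, but they give the first call to different roles.

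At stake is whether a low-risk participant receives the clinician reassessment that one section requires, and whether each role knows that the call is its own. This is a participant-protection matter. It does not touch the estimand, the power or the analysis.

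**Working it through.** No arithmetic applies to the conflict itself. The check sets side by side every section that says what follows a finding of suicide risk in a session.

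| Point | In-Session Measures; Clinical Deterioration | Protections for Participants with Suicide Risk |
|---|---|---|
| Trigger for clinical backup | Moderate or high C-SSRS risk | Risk shown by electronic session measures, or disclosed ideation; no level stated |
| Who starts the contact | Research Associate (In-Session Measures); not named (Clinical Deterioration) | Group leader |
| Immediate clinician reassessment at low risk | Not stated | Required before any tier is applied |
| Low or mild steps | Emergency-service call and family encouraged (In-Session Measures); stays in ROST; weekly monitoring | Emergency-service call and family encouraged; follow-up until risk is minimal |
| Labels | Low, moderate, high (C-SSRS) | Mild, moderate, high |

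1. *Can risk in the suicide-risk section mean only moderate or high?* The text does not support that. Disclosure of ideation is enough by itself. The contact and reassessment come before the tiers, and the lowest tier, Mild, describes ideation with no current plan and low intent. A participant who ends up in that tier has therefore already passed through the reassessment.

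2. *Does the cross-reference settle it?* No. The human-participant protection material to which In-Session Measures points contains both Clinical Deterioration, which repeats the moderate-or-high threshold, and the suicide-risk section, which has no threshold.

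3. *Are the two named persons the clinical backup?* The names are removed from the public copy, so this is inferred. Clinical Backup, In-Session Measures and Potential Risks each give two named persons in that role, and the suicide-risk section gives two named persons doing that job.

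4. *Do the labels line up?* Low and Mild sit at the same place on two three-level ladders and carry similar steps, but no sentence equates them.

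5. *How often could it arise?* With the 42 ROST participants planned to take part and 8 sessions, the item-9 check would be run up to 42 × 8 = 336 times. The share of checks that would be positive and then classed low risk is not given, so the number of affected participants cannot be derived.

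**The case against.** The best case for the plan is that the sections can be read together. Neither In-Session Measures nor Clinical Deterioration says that backup is reached only at moderate or high risk, and neither forbids the call at low risk. On that reading the suicide-risk section adds a group-leader call, staff can follow both, and the cross-reference marks it as the fuller rule. Other safeguards also apply: investigators are told at once whatever the level, and backup is open to group leaders whenever suicidality is present. Training materials that may settle the routing are not in the documents.

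Much of this stands, and it rules out three stronger readings that a reader might infer:

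- *That the low-risk action is undefined.* It is stated, and the encouragement and the monitoring until risk is minimal largely agree across sections.
- *That the Research Associate handles low risk alone.* On site, the group leader also reviews the score and risk level, although the low-risk action is assigned to the Research Associate.
- *That different instruments trigger the two rules.* The electronic session measures in the suicide-risk section are most naturally the PHQ-9 and C-SSRS of In-Session Measures. What remains is an unmapped label.

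The compatibility argument does not remove the conflict. Staff who do everything that In-Session Measures and Clinical Deterioration ask for a low-risk participant will still omit the immediate reassessment that the suicide-risk section requires. Informing the investigators is not the same as a clinician reaching the participant. The question of which role makes the call also remains at moderate and high risk.

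**Conclusion.** The inconsistency is real and narrow. The sections disagree on two things: whether a clinician must reassess a low-risk participant at once, and whether the Research Associate or the group leader starts the contact. The missing link between the C-SSRS low level and the Mild tier adds to the uncertainty.

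The conclusion rests on two readings: that the removed names in the suicide-risk section are the clinical backup, and that a C-SSRS low classification counts as risk under that section. The first is an inference from role. The second follows from the trigger and from the order of the steps.

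The rule applies to any ROST participant with a positive item 9 and a low C-SSRS level at any of the 8 sessions; how many that will be is unknown. A reader might also infer that low-risk participants will go without clinician review. The documents do not show that. They show that the outcome depends on which section staff follow. The point should be corrected on participant-safety grounds, and no statistical result depends on it.

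**What to change.** Reconcile In-Session Measures, Clinical Deterioration and Protections for Participants with Suicide Risk, including its tier list, so that one rule states:

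- for each risk level, which role contacts clinical backup and when;
- for each risk level, whether and when clinical backup reassesses the participant;
- how the C-SSRS levels map to the Mild, Moderate and High tiers.

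The other sections can then refer to that rule. Which rule stands is for the sponsor's clinical team to decide; this review takes no view on it. The cost is protocol wording and a line in staff training, with no change to sample size, data collection or analysis.
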